EMPA-TROPISM Trial: Are the "cardiac benefits" of Empagliflozin independent of its hypoglycemic activity?

PI: [name]

NCT03485222

Document Date: Nov 28, 2017

Icahn School of Medicine at Mount
Sinai Mount Sinai Beth Israel
Mount Sinai Brooklyn
The Mount Sinai Hospital Mount
Sinai Queens
New York Eye and Ear Infirmary of
Mount Sinai
Mount Sinai St. Luke's Mount Sinai
West

**Program for the Protection of Human
Subjects**
Institutional Review Boards
Mount Sinai Health System
[name]
[name] T [name]
F [contact]
[contact] icahn.mssm.edu/pphs

Table of Contents

1. Title	1
2. Background	2
3. Research Personnel.....	4
4. Subjects - Enrollment	5
5. Subjects - Setting and Resources	5
6. Subjects - Populations	5
7. Subjects - Participation	6
8. Subjects - Risk and Benefits	7
9. Procedures - Narrative	10
10. Procedures - Details.....	12
11. Consent - Obtaining Consent.....	13
12. Data – Collection, HIPAA and Storage.....	14
13. Data - Safety Monitoring	15
14. Drugs / Biologics	18

1. Title

Protocol Title

EMPA-TROPISM Trial: Are the "cardiac benefits" of Empagliflozin independent of its hypoglycemic activity?

Principal Investigator

[name]

Primary Department

Medicine - Cardiology

Application Initiated By

[name]

Lay Summary

Empagliflozin is the first drug that improves glucose control and has cardiovascular benefits. A recent trial has shown significant reductions in adverse events. Cardiovascular mortality and hospitalization were reduced by empagliflozin given on top of standard-of-care therapy in diabetics. Some investigators have suggested that these benefits are independent of its glucose lowering effect and thus, Empagliflozin could be considered a "cardiac" drug.

Our overall hypothesis is that the benefits attained from empagliflozin were at least in part, mediated by a glucose- independent mechanism. Thus, we are proposing to conduct a study to investigate the postulated benefits of empagliflozin vs placebo involving non-diabetic patients with heart failure.

2. **Background**

Objectives

Our overall hypothesis is that the benefits attained in the EMPA-OUTCOME were at least in part, mediated by a glucose-independent mechanism. Thus, to demonstrate the existence of pleiotropic (non-glucose dependent) effects associated with empagliflozin administration, we are proposing to conduct a pilot randomized, double blind, placebo- control, single-center study to investigate the postulated "cardiovascular" benefits of empagliflozin 10mg/day vs placebo involving non-diabetic HF patients with reduced ejection fraction.

Background

Empagliflozin is the first glucose-lowering agent that not only improves glycemic control but also has cardiovascular benefits. The recent EMPA-OUTCOME trial has shown significant reductions in major adverse cardiac events (MACE), cardiovascular mortality, and hospitalization for Heart Failure (HF) with empagliflozin given on top of standard-of-care therapy for T2DM patients with cardiovascular disease (CVD). Some investigators have suggested that these benefits may be independent of its hypoglycemic activity and thus, Empagliflozin could be considered a "cardiac" drug. This hypothesis has emanated from the data of the EMPA OUTCOME clinical trial.

Empagliflozin treatment did not have any effects on the rate of the traditional atherothrombotic events. The dramatic change driving the superiority of the primary composite outcome (major adverse CV events) was a significantly lower CV death rate (38% relative risk reduction). In addition, there were also an impressive 35% and 38% relative risk reductions in hospitalization for heart failure (HF) and death from any cause. Of the major interest is that these benefits occurred in the absence of any major differences in glycemic, lipid, or blood pressure (BP) control. Management of concomitant HF in T2DM is particularly challenging, as some glucose-lowering agents, such as TZDs, are contraindicated in patients with HF. Until recently, there was an unmet need for an oral agent that improved glycemia as well as provided CV benefits, including decreasing HF in patients with, or at risk of, CVD.

Type 2 diabetes mellitus (T2DM) is one of the most common chronic health conditions in the United States; it affects approximately 10% of adults with up to one-quarter being undiagnosed. T2DM is associated with substantial cardiovascular (CV) morbidity and mortality. Heart failure (HF) is a frequent co-morbid condition associated with poor prognosis in diabetes, particularly among older patients. HF accounts for more than 1 Million hospitalizations annually in USA. In addition, HF hospitalizations are associated with significant high risk of post-discharge mortality and recurrent hospitalizations. Almost one-half of patients will be re-hospitalized within 6 months and one-third will die within 12 months of discharge. Median survival after HF diagnosis is about 5 years, and is similar for HFpEF and HFrEF patients. Diabetes as co-morbidity multiplies risk of hospital admissions in HF patients.

Management of concomitant HF in T2DM patients is particularly challenging. Some glucose-lowering agents, such as TZDs, are contraindicated in patients with HF. Until recently, there was an unmet need for an oral agent capable of improving glycaemia as well as providing CV benefits, including mitigating HF in patients with or at risk of CVD. There are a couple of characteristics that single out the SGLT2 inhibitors from other hypoglycemic drugs. One is their low hypoglycemic risk since their act on the urinary excretion of glucose without interfering with the physiologic response to hypoglycemia, and the other is their "positive" cardiovascular effects such as lowering blood pressure, arterial stiffness, urinary microalbuminuria and triglycerides while increasing HDL-cholesterol levels. The recent EMPA-OUTCOME trial showed significant reductions in major adverse cardiac events (MACE), CV mortality, and hospitalization for HF with Empagliflozin when given on top of standard-of-care therapy for T2DM and CVD. Therefore, the combination of the above-mentioned observations led to some investigators to suggest that these benefits may be, at least in part, independent of its hypoglycemic activity and thus, Empagliflozin could be considered a "cardiac" drug.

Our overall hypothesis is that the benefits attained in the EMPA-OUTCOME were at least in part, mediated by a glucose-independent mechanism. Thus, to demonstrate the existence of pleiotropic (non-glucose dependent)

effects associated with empagliflozin administration, we are proposing to conduct a pilot randomized, double blind, placebo- control, single-center study to investigate the postulated "cardiovascular" benefits of empagliflozin 10mg/day vs placebo involving non-diabetic HF patients with reduced ejection fraction.

Primary Endpoints

The primary end-point will be to determine whether empagliflozin mitigates changes in LV end systolic volume (ESV) or LV end diastolic volume (EDV) in HF patients without diabetes when compared to placebo. We have chosen LV volume because it is the strongest predictor of adverse cardiovascular outcomes even after adjusting for LVEF and MI size (White HD *Circulation*. 1987;76:44–51 and Migrino RQ *Circulation*. 1997;96:116–121).

Secondary End-points

1. To determine changes in LV mass, LV-EF and remodeling index (LV mass/LV-EDV) with empagliflozin compared with placebo.
2. To determine if there is a change in left atrial volume (an accurate indicator of chronic increase in LV filling pressures) with empagliflozin compared with placebo.
3. To determine if there is a change in right ventricular (RV) EDV, RV-ESV and, RV-EF with empagliflozin compared with placebo.
4. To determine if there is a change in cardiac interstitial fibrosis as assessed by T1 mapping with empagliflozin compared with placebo.
5. To determine if there is a change in VO₂ Oxygen consumption with empagliflozin compared with placebo.
6. To determine if there is a change in Visceral and epicardial fat as measured by CMRI with empagliflozin compared with placebo.
7. To determine if there is a change in arterial stiffness measured by CMRI with empagliflozin compared with placebo.
8. To determine if there is a change in body composition analysis (BCA anthropomorphic measurements) with empagliflozin compared with placebo.
9. Effect of the treatment on several cardiovascular and inflammatory biomarkers with empagliflozin compared with placebo.
10. To determine if there is a change in exercise tolerance by the 6 min walk test with empagliflozin compared with placebo.
11. To determine if there is a change in the patient-reported quality of life by the Minnesota Living with HF and SF-36 questionnaires.

Safety and Tolerability

Patients will be monitored for signs of hypoglycemia, urinary tract infections, bone fractures, diabetic ketoacidosis and thromboembolic during the follow-up period. We will also assess survival, hospitalizations and HF worsening (more visits, increase in prescription of diuretics, etc).

3. **Research Personnel**

Name/Department

[name] / Medicine - Cardiology
[name] / Cardiology
[name] / Medicine - Cardiology
[name] / Medicine - Cardiology
[name] / Medicine - Cardiology
[name] / Medicine - Cardiology
[name] / Medicine - Endocrinology
[name] / Medicine - Cardiology
[name] / Medicine - Cardiology
[name] / Medicine - Cardiology
[name] / Cardiology

Role/Status

Principal Investigator
Co-Investigator
Co-Investigator
Co-Investigator
Co-Investigator
Co-Investigator
Co-Investigator
Co-Investigator
Co-Investigator
Co-Investigator
Co-Investigator

4. Subjects - Enrollment

Site Name

Icahn School of Medicine at Mount Sinai

Subjects To Be Enrolled

100

Total Number of Subjects Needed To Complete Study

80

5. Subjects - Setting and Resources

Feasibility of Meeting Recruitment Goals

HF patients will be identified from the HF clinic at Mount Sinai and the Mount Sinai Consortium database for patients with chronic heart failure. The MSSM consortium includes the Mount Sinai Medical center of Manhattan, Elmhurst Hospital in Queen, the VA Bronx and the Mount Sinai Saint Luke's Hospital in Harlem and the Mount Sinai-West Hospital (former Roosevelt Hospital).

The Consortium's database contains more than 10,000 HF patients. This proposal involves non-diabetic HF patients and given the common co-existence of diabetes affecting to 40-50% of HF patients; the database still offers us a potential 5,000 HF patients that could be candidates for enrollment in our study.

Facilities to be Used for Conducting Research

Consent Form and blood collection: Atran Bldg 6th Room 20 CMRI - Lauder Imaging facilities

O2 consumption and Vo2 consumption: Cardiopulmonary Exercise laboratory on Guggenheim 6.

6. Subjects - Populations

Inclusion Criteria

Patients should meet the following inclusion criteria:

1. Ambulatory patients age more than 18 years
2. Diagnosis of Heart failure (NYHA II to III)
3. LVEF<50% on echocardiography or CMRI
4. Have stable symptoms and therapy for HF more than 1 week.

Exclusion Criteria

1. Pregnant or lactating women.
2. Any history of diabetes by medical history or by any of the established criteria by the American Diabetes Association. It also includes patients with history of diabetes in remission.
3. ACS or cardiac surgery within the last 3 months.
4. Cancer or any other life-threatening condition.

5. Glomerular Filtration Rate < 30 ml/Kg/min.
6. Use of continuous parental inotropic agents.
7. Systolic BP < 90 mm Hg.
8. Recreational drugs and /or excessive alcohol.
9. Psychiatric disease incompatible with being in study.
10. Any contraindication to MRI procedures.
11. Any other medical or physical condition precluding the subject's participation.

7. Subjects - Participation

Duration of an Individual Subjects Participation in the Study

6 months

Duration Anticipated to Enroll All Study Subjects

20 months

Estimated Date for the Investigators to Complete This Study

3-5 years

Procedures for Subjects to Request Withdrawal

You may stop taking part in this research study at any time without any penalty. This will not affect your ability to receive medical care at any of the Mount Sinai Health System hospitals or to receive any benefits to which you are otherwise entitled.

If you decide to withdraw your consent, we ask that you contact [name] [name], and let him know that you are withdrawing from the study. His mailing address is the Icahn School of Medicine at Mount Sinai, [name]. If you wish to withdraw your authorization as well you must contact [name] in writing at the Icahn School of Medicine at Mount Sinai, [name].

You may also withdraw your permission for the use and disclosure of any of your information for research, but you must do so in writing to the Principal Investigator at the address on the first page. Even if you withdraw your permission, we may still use the already collected information if it is necessary to complete the study. Your health information may still be used or shared after you withdraw your authorization if you should have an adverse event from participating in the study.

Procedures for Investigator to Withdraw Subjects

The study doctor, the sponsor or the institution may stop your involvement in this research study at any time without your consent. This may be because the research study is being stopped, the instructions of the study team have not been followed, the investigator believes it is in your best interest, or for any other reason. If specimens or data have been stored as part of the research study, they too can be destroyed without your consent.

Participants Will Be Recruited

Yes

Recruitment Method(s)

Clinical Practice, Registry/Bank, Records

How Participants Will Be Identified

In all disclosures outside of Mount Sinai, you will not be identified by name, social security number, address, telephone number, or any other direct personal identifier unless disclosure of the direct identifier is required by law. Some records and information disclosed may be identified with a unique code number. The Principal Investigator will ensure that the key to the code will be kept in a locked file, or will be securely stored electronically. The code will not be used to link the information back to you without your permission, unless the law requires it, or rarely if the Institutional Review Board allows it after determining that there would be minimal risk to your privacy.

Who Will Initially Approach Potential Participants

Treating Physician, Clinic Personnel

How Research Will Be Introduced to Participants

Research will be introduced by the primary physician or physicians from the Heart Failure Program at ISMMS. They will be informed of the significant cardiac benefits obtained in heart failure and diabetic patients. In addition, we will tell the participants that the objective of the study is to investigate whether the benefits seen in the HF and diabetic population could be extrapolated to HF patients independently of their diabetic status.

How Participants Will Be Screened

All approached participants will have a diagnosis of HF. Upon signing of the informed consent form, a blood sample will be collected and analyzed to assure that participants fulfill ALL the inclusion criteria but NONE of the exclusion criteria. We will ask questions about their medical history and perform a physical exam that includes weight, height, body temperature, blood pressure, pulse rate, and EKG. In addition, we will collect blood and urine to check for routine lab tests, hepatitis B and C, use of recreational drugs and HIV test. The results of the drug testing will NOT be placed in the participant's medical record.

8. Subjects - Risk and Benefits

Risks to Subjects

Empagliflozin is approved by the FDA for the treatment of high levels of glucose in diabetic subjects. This drug has been studied in tens of thousands of patients and, despite its well-established benefits, the adverse effects observed and that could very rarely affect you are:

- Low sugar levels manifested as blurry vision, accelerated cardiac pulse, irritability, nervousness, headaches, shivers, sweating, tireless, tingles and/or appetite loss.
- Blood pressure lowering manifested as headache, dizziness, confusion, irritability, sweat and irregular cardiac pulse.
- Dehydration manifested as headache, dizziness, confusion, weakness specially when standing up.
- Ketoacidosis manifested as headache, fatigue, nausea/vomiting, stomach ache, breathing difficulties, abdominal pain, urinating urges, appetite loss.
- Urinary infections (penis in men and vagina in women) manifested as frequent urination urges, irritation while urinating, blood and/or bad smell of the urine, pain in the stomach and/or pelvis.
- Allergies manifested as cutaneous rushes, inflammation and/or itching in the face, tongue and throat as well as dizziness and breathing difficulties.
- In case you experience any of these symptoms, stop taking the study drug and immediately contact the investigators at the phone number provided below in this document.

- There are no reports of any psychological or social risks associated with the treatment.
- The risks of a blood draw include pain, bruising, and the slight possibility of infection at the place where the needle goes in. Some people feel dizzy or may faint during or after a blood draw.

Description of Procedures Taken to Lessen the Probability or Magnitude of Risks

Upon randomization, all participants will be invited to come to the MSMC at 1- and 3-months post-therapy initiation to assure the safety of the assigned treatment.

They will be instructed on the symptoms typical of the potential risks associated with the treatment. In case of any doubt, they should stop taking the drug and call the investigators. In conditions of significant discomfort or pain, they should go to the closest Emergency Room and notify the investigators.

Provisions for Research Related Harm / Injury

If you believe that you have suffered an injury related to this research as a participant in this study, you should contact the Principal Investigator, [name] [name] or [name], at [contact]. If you are injured or made sick from taking part in this research study, medical care will be provided. Generally, this care will be billed to you or your insurance in the ordinary manner and you will be responsible for all treatment costs not covered by your insurance, including deductibles, co-payments and coinsurance. This does not prevent you from seeking payment for injury related to malpractice or negligence. Contact the investigator for more information.

Expected Direct Benefit to Subjects

It is important to know that you may not get any benefit from taking part in this research. However, possible benefits may be a reduction in the frequency of hospitalization and an improvement of the symptoms associated with heart failure in the group receiving the study treatment.

Benefit to Society

It is hoped the knowledge gained from this study will be of benefit to others in the future.

Provisions to Protect the Privacy Interests of Subjects

As part of this research project, it will be necessary for the research team and others to use and share some of the private protected health information. Consistent with the federal Health Insurance Portability and Accountability Act (HIPAA), we are asking your permission to receive, use and share that information.

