Neither you nor the study doctor will choose what study treatment you get. You will have an equal chance of being assigned to either study treatment group. One group will receive a pill of empagliflozin (10mg/day) while the other (placebo-control) group will receive a sugar pill without active medicine. The study pills will be taken orally and preferably at the same time every day. The study pill will be taken in addition to all the drugs prescribed by your physician. You will be provided detailed instructions on how to take your study pills in person during this visit.

The treatments in this study will be 'blinded', meaning neither you nor the study investigators will know which study treatment you are getting. This information could be obtained in an emergency however, you will not be told which study treatment you are getting, but your study doctor will know.

At the end of this visit, we will provide you with a supply of the assigned pills and you will be allowed to go home. We will schedule your next visit within 1-2 weeks of visit 2.

Visit 3 Safety: This visit will last approx. 1 hour. You will be asked to report to the 6th Floor of the Atran Building at the MSMC in a fasting state. During this visit, we will perform the same procedures as per the visit 1. The most important reason for this visit is to monitor the safety and efficacy of the medicine that you are taking. During this visit, we will record your vital signs (weight, height, body temperature, blood pressure, pulse) and collect one blood sample (15mls or 1 table spoon) for routine lab test (lipids, glucose, liver enzymes, etc.). We will ask you questions about your health since your last visit. Thereafter, we will provide you with a supply of the assigned pills and your visit will end.

Visit 4 Maintenance: This visit will last approx. 1 hour. Within 12-14 weeks of the previous visit, you will be asked to report to the 6th Floor of the MSMC in a fasting state. The reason for this visit is to continue monitoring the safety and efficacy of the medicine that you are taking. We will repeat the procedures done during your previous visit (i.e. record your vital signs and collect one blood sample for routine lab test) and ask you questions about your health status since your last visit. Thereafter, we will provide you with a supply of the assigned pills and your visit will end.

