Visit 5 Final: This will be the last visit and will have an approx. duration of approx. 4 hours. You will be asked to report to the 6th Floor of the Atran Building at the MSMC in a fasting state. During this visit, we will repeat the procedures performed during visit 2. The procedures will be: Magnetic resonance imaging, Oxygen consumption, 6-minute walking test, the Minnesota questioner and collect one blood sample (15 mls or 1 table spoon). We will record your vital signs (body weight, height, body temperature, blood pressure, pulse) and EKG to check your health status. The comparison of the results obtained during visit 2 and visit 5 will allow us to delineate the effects of the study drug. At the end of this visit, your participation in the study will end.

Description of Procedures Being Performed

Cardiac Magnetic Resonance Imaging (CMR): CMR studies will be performed at the Cardiac Imaging Facilities of the Mount Sinai Heart under the direction of [name] (Investigator of the proposal). Images will be acquired with a 3.0 Tesla magnet (Achieva, Philips Medical Systems, Netherlands). Steady-state free precession short axis images (TR 3.6 ms, TE 1.6 ms, flip angle 45°, field of view 250 x 250 mm, SENSE factor 3, voxel size 1 x 1 x 5 mm, no gap, number of averages 3, bandwidth 1286 Hz, 12 lines per segment) from the LV base through LV apex will be used for the quantification of LV volumes, ejection fraction and mass. Late gadolinium enhancement (LGE) will be performed 15 minutes after the administration of gadolinium (Magnevist, 0.2 mmol/kg) using an inversion-recovery fast gradient echo sequence (TR 9 ms, TE 5.4 ms, TI optimized to null normal myocardium, gating factor 3, field-of-view 250 x 250 mm, pixel size 1 x 1 x 5 mm, SENSE factor 3, number of averages 3, bandwidth 232 Hz, TFE factor 16). A Look-Locker sequence will be performed before and 10 minutes after gadolinium administration to evaluate interstitial myocardial fibrosis using the T1 mapping technique. All CMR images will be blindly analyzed using commercially available software (Extended MR Workspace, Philips Medical Systems, Netherlands). Epicardial and endocardial

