The PI will serve as Investigator of Records (IoR). He will appoint a senior member of his clinical research staff to serve as Study Coordinator, who will work closely with the Regulatory Manager of the Mount Sinai Heart, to monitor case report forms (CRFs) on a weekly basis, and the SMC will meet every 6 months, or more frequently is needed, during the study to review CRFs.

The Study Coordinator will verify data collected on case report forms against source documents. Source documents can include any of the following: hospital records, research records, laboratory values, subject diaries, checklists, pharmacy records, data recorded from automated instruments (such as ECG), medical transcriptions, magnetic media images, and x-rays.

The Study Coordinator will work closely with the Mount Sinai Heart Regulatory Manager to compare the procedures defined in the protocol as well as regulatory requirements to ensure data integrity. Internal auditing includes the review of all the regulatory documents; (IRB, regulatory agency correspondence) and clinical records. The IoR and the Study Coordinator will ensure the following regulatory requirements are met:

- Verify investigator qualifications.
- Review PI and sub-investigator CV's and registrations and verify documentation was current at time of study visit.
- Verify current certifications and lab normal ranges protocol-required procedures.
- Verify equipment not covered under CLIA or CAP certifications are adequately maintained and review certifications.
- Verify facilities remain adequate throughout the trial.
- Ensure drug dispensation and storage complies with regulatory requirements.
- Verify documentation in the master file of receipt of disposition/use and return of product.
- Verify the master file contains guidelines for handling product.
- Verify the site maintains records that indicate product has been supplied only to eligible subjects at protocol specified doses.
- The investigator's records for study drug shipping receipts including lot number and quantity (if applicable).
- Shipping receipts to other sites (if applicable).
- Review of dispensing logs including the subject initials, number, dose or quantity and person dispensing.
- Temperature log.
- Return receipts.
- Verify that the protocol or the master file documents provides the necessary instructions to the patients on how to use, handle, store, and return drug.
- Verify the site is following the approved IRB protocol.

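### Exclusion criterion 5 states its renal threshold in ml/kg/min, a unit in which no adult could reach 30, and nothing elsewhere in the document corrects it

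*Combined protocol and SAP*

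**What the plan says.** The combined protocol and SAP sets one renal criterion. In section 6 (Subjects - Populations), Exclusion Criteria, item 5 reads "Glomerular Filtration Rate < 30 ml/Kg/min".

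Section 7, under the heading on how participants will be screened, makes this an operating rule. A blood sample is taken after consent to make sure that "participants fulfill ALL the inclusion criteria but NONE of the exclusion criteria". The laboratory work is described only in general terms: "we will collect blood and urine to check for routine lab tests, hepatitis B and C, use of recreational drugs and HIV test". It names no GFR method, creatinine measurement or reporting unit.

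Two other exclusions could bear on renal suitability, but neither gives a figure. Item 10 is "Any contraindication to MRI procedures", and item 11 is a catch-all for other conditions that would prevent participation. No rationale is given for item 5.

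**The concern.** GFR is a volume filtered per unit of time. It is usually stated as an absolute flow or scaled to body surface area. Item 5 instead divides by body weight while keeping a number of 30, and on that scale 30 lies far above anything an adult kidney can do. Because it is an exclusion below the threshold, the literal rule removes everyone.

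The practical stake is smaller than that but real. Nobody can enrol a patient without replacing the printed unit, and the document does not say with what. Patients near the cut-off may then be included or excluded according to the unit the screener chooses, and the eligibility decision cannot be checked against the written text.

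**Working it through.** **Inputs from the document.** Threshold and unit: 30 ml/kg/min, exclude if below (section 6, item 5). Planned enrolment: 100 (section 4). The document derives no other figure from this threshold, so there is no calculation of its own to reproduce.

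**Assumptions not in the document.** Adult weight 50 to 110 kg, widened to 40 to 150 kg as a check. Whole-body GFR of at most about 150 ml/min, a deliberately generous ceiling. For step 4, the usual indexing reference of 1.73 m² and body surface areas of 1.5 and 2.2 m².

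**Step 1: convert the threshold to a whole-body flow.** Flow (ml/min) = 30 × weight (kg).

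| Weight (kg) | 30 ml/kg/min as ml/min | Multiple of 150 ml/min |
|---|---|---|
| 40 | 1,200 | 8 |
| 50 | 1,500 | 10 |
| 70 | 2,100 | 14 |
| 110 | 3,300 | 22 |
| 150 | 4,500 | 30 |

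At 70 kg this is 2,100 × 1,440 / 1,000 = 3,024 litres filtered per day.

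**Step 2: check in the other direction.** Per-kg GFR = whole-body GFR / weight. The most favourable case under the assumptions is 150 / 40 = 3.75 ml/kg/min. At 70 kg the ceiling gives 150 / 70 = 2.1. Both are far below 30.

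**Step 3: apply the rule.** Every adult has a value under 30 ml/kg/min, so every candidate meets item 5. Section 7 requires that no exclusion be met, so the number eligible out of the planned 100 is zero on the literal reading. The GFR ceiling would have to be 8 to 30 times higher to change this.

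**Step 4: does the choice of replacement unit matter?** Keep the printed number 30 for illustration only, and compare absolute ml/min with a body-surface-indexed value. Absolute = indexed × body surface area / 1.73.

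- Indexed 26 at 2.2 m²: 26 × 2.2 / 1.73 = 33 ml/min. Excluded on the indexed scale, not excluded on the absolute scale.
- Indexed 33 at 1.5 m²: 33 × 1.5 / 1.73 = 29 ml/min. Not excluded on the indexed scale, excluded on the absolute scale.

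The two scales disagree between these limits:

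- At 2.2 m²: indexed values from 30 × 1.73 / 2.2 = 23.6 up to 30.
- At 1.5 m²: indexed values from 30 up to 30 × 1.73 / 1.5 = 34.6.

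How many candidates would fall in these bands cannot be computed, because the document gives no distribution of GFR in the source population.

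**The case against.** The strongest reply is that the error announces itself. A rule that excludes every adult cannot be adopted by mistake, so a screener will recognise a slip and read a conventional unit. The trial is single-center, with all research activity at one medical center, which limits how far reporting could vary. No calculation in the plan uses the figure. All of this stands, and it is why the point is a correction and not a challenge to the design. It does not remove the point, because the text never says which conventional unit is meant and step 4 shows that the choice can change eligibility.

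Four stronger readings are tempting and are not supported.

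- **That patients with poor renal function would be let in.** The printed rule errs in the restrictive direction and would not by itself admit anyone.
- **That item 5 is the safety cut-off for gadolinium and study drug.** Both exposures occur in the trial, but the document gives the criterion no purpose and links it to neither.
- **That it is the only renal safeguard.** It is the only numeric renal threshold. Items 10 and 11 and the routine laboratory tests leave room for judgement, although none states a renal value.
- **That every enrolled patient would count as a protocol violation.** The monitoring checklist in section 13 says "Verify the site is following the approved IRB protocol", but this is a generic line. It does not show that an auditor would enforce an impossible unit literally instead of asking for a correction.

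**Conclusion.** The unit in item 5 is wrong as written and should be corrected. The printed threshold is 8 to 30 times a generous adult GFR ceiling across 40 to 150 kg, so the conclusion does not hinge on the exact weight or ceiling assumed. Read literally, it excludes all candidates. In practice it leaves the unit to whoever screens, with possible misclassification confined to patients near the cut-off. The size of that last effect is not known from the document, and the worked examples rest on assumed body sizes and the usual indexing reference. The most likely cause is a transcription slip. Sample size, power, type I error and the planned analyses are unaffected.

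**What to change.** The investigators should confirm the cut-off they intended and restate item 5 in the unit in which the study laboratory reports GFR, with that definition applied identically to every candidate at screening. Naming the estimating equation at the same time would be useful added detail, but its absence is not part of the error. Which renal cut-off is appropriate is a clinical decision for the investigators.

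The cost is a one-line correction to the protocol text. It needs no change to the design or the analysis plan.
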